3.10. Data analysis

Analysis will be undertaken by the PHE Behavioural Insights Team working with the Statistic Unit, PHE National Infection Service. Our main analysis will be by intention to treat allocation for the primary and secondary outcomes. We will use logistic regression to investigate the main effect of the interventions and their interaction. The model also will include provider, local authority and school effect to take into account extra variation that was not explained by intervention and other confounder variables. In the models, we will also investigate the impact of secondary factors such as school-year (to determine if there's any greater impact for those that have not previously

received an invitation letter) and inequalities (e.g. IMD quintile, proportion of children eligible for free school meals, proportion of children not with English as first language).

We will also undertake a per-protocol analysis of the primary and secondary outcomes, including in the analysis only those schools in trial arms 1 and 3 who implemented the request to send a reminder message with high fidelity to the request and those schools in trial arms 2 and 4 who did not send a reminder request. While the intention to treat analysis will be a composite of the effectiveness of reminders and the prevalence of SMS/email systems, the per-protocol analysis will enable these components to be disentangled.

We will analyse the invitation letters used in non-trials areas by coding the letters using the Theoretical Domains Framework (TDF). This will enable us to assess their behavioural-insight framing and fidelity to the new template letter. We will analyse whether those areas that used a letter similar to the new template had i) higher uptake and ii) greater change in uptake from to last year, compared to areas that used a dissimilar letter.

4. Study sponsorship and approvals

This study has been reviewed by the PHE Research Ethics and Governance Group to gain approval for PHE to act as the study sponsor.

Health Research Authority (HRA) approval has been sought, which includes ethical (opinion provided through UK Health Departments' Research Ethics Service), governance and legal review. (HRA/ethics number xxxxxxxx).

The trial has been registered on clinicaltrials.gov, trial number xxx.

5. Main risks and mitigation

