3.1. Design overview

This is a 2x2 factorial design, open-label, randomised (at school level) trial of invitation letters and SMS/email reminders for childhood flu immunisation (Figure 1).

Figure 1. Randomisation and trial arms

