3.2. Primary and Secondary outcomes

The primary outcome for this study is the proportion of children in school years 1-3 who receive influenza immunisation as part of the national childhood immunisation programme.

We will also look at a number of secondary outcomes to determine the effect of the interventions on influenza immunisation in different age groups and on consent-giving. The secondary outcomes are:

- 1) Proportion of children who receive influenza immunisation
 - a) in school years 4-6ⁱⁱ
 - b) in Receptionⁱⁱⁱ
 - c) in each individual year group
- 2) Proportion of children for who consent is neither given nor withheld (i.e. non-responders)
 - a) in school years 1-3
 - b) in school years 4-6
 - c) in each individual year group

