3.7. Power calculations

Given that all school-based flu immunisation programmes send invitation letters to parents, even a small increase in uptake from changes to the phrasing of the letter will be worthwhile. Furthermore, given that participating areas will be sending letters to all parents of eligible children it is simpler to include all schools within a participating local authority area. Including a number of providers, which cover 13 local authorities, increases the generalisability of our research findings. We are therefore starting from the position of having potentially ~1700 schools to include in the trial. Sample size calculations are not therefore appropriate as we are not sampling from the participating areas, but rather including the full population. We can however explore the potential power of our study.

Although our allocation will be stratified by local-authority, to explore the potential power of the study we have made the crude assumption that all strata are equal (i.e. that there is no variation between local authorities). We therefore used *sampsi*

followed by the *sampclus* commands in Stata to estimate our study power. We determined the number of schools using data on schools by local authority available from Compare school and college performance website^{iv}. We used 2015/16 data provided for Leicester, Leicestershire and Rutland to estimate the average size of each cluster (i.e. average number of children in school years 1-3) (excluding schools with fewer than 20 pupils in years 1-3). The average size of cohort was 110, and we have therefore conservatively used 100 as our estimate. We used an average vaccine uptake of 63.0% (SD 16.2%) in our power calculations.

We do not have a known value for the intra-class correlation (ICC). Shackleton et al⁷ estimated that ICC values for health outcomes in adolescent children ranged from ICCs ranged from 0.01 to 0.21 depending on the outcome being measured and the country. Within Britain, ICC ranged from 0.01 to 0.15 depending on health outcome, with the highest correlation for regular smoking. These health outcomes are not directly comparable with vaccine uptake or primary school age children (for which the behaviour is actually one of the parents) but nonetheless provide an anchor point around which to explore in the absence of more relevant estimates. We used 0.025 as our basic estimate.

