3.9. Data collection

Data are collected by immunisation providers as part of the routine programme. While data on the number of vaccines administered and denominators (i.e. not including data on consent) will be submitted centrally at the end of November 2016, December 2016, January 2017 and February 2017 only the final data submission in March 2017 will provide school-level data and data on consent as well as uptake.

Many areas use a spreadsheet generated by PHE which records individual level data for local management and enables data to be cumulated to the different levels required (e.g. school, local authority) and includes data on consent. These different

cumulative levels can be submitted as required, without the inclusion of individual-level data.

School-level data by school year are routinely submitted to PHE. We will obtain final school-level data from PHE at the national level in March 2017. These data will then be linked with the allocation list for analysis using the School Unique Reference (Figure 2). We will ask providers to submit an interim school-level data extract (e.g. in November) to enable the analysis to be fully planned (i.e. statistical analysis code written) ahead of the availability of final data. This will be important to enable the timely production of results which can then inform next year's programme, however it will not be compulsory if an area is not able to provide these interim data. This analysis will be seen only by a quorum of the investigators and they will not be results released to the wider study team or beyond so as not to impact on the final uptake data. No individual-level data or Personal Identifiable Information will be collected.

Data on characteristics of the schools will be obtained from publically available sources and linked to the immunisation database. This will include data from gov.uk, Compare school and college performance website^v on characteristics such as the proportion of children on free school meals, pupils with English not as the first language, religious denomination of the school and type of school. The postcode of schools will be linked to Index of Multiple Deprivation (IMD) data to obtain a deprivation indicator, quintile or decile ranking, for the school location.

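### With no variance term below school, the intervention-by-school-year comparison gets too small a standard error wherever year groups of one school vary beyond binomial error

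*Combined protocol and SAP*

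**What the plan says.** Section 3.1 describes a "randomised (at school level) trial of invitation letters and SMS/email reminders", so all year groups of a school are in the same arm. Section 3.9 states that "School-level data by school year are routinely submitted to PHE", so a school contributes several counts, one per year group.

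For the analysis, section 3.10 says: "We will use logistic regression to investigate the main effect of the interventions and their interaction". It continues: "The model also will include provider, local authority and school effect to take into account extra variation that was not explained by intervention". It then adds: "In the models, we will also investigate the impact of secondary factors such as school-year", and gives the reason: to see whether the impact is greater in children who have not had an invitation letter before. That is a question about an interaction between intervention and school-year.

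School is the lowest level named. The section mentions no school-by-year term, no overdispersion parameter and no robust standard error. It does not say whether the school effect is fixed or random.

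**The concern.** A school effect takes up what all year groups of a school have in common. It does not take up differences between year groups of the same school, and this is so whether the effect is fixed or random. Once it is in the model, a comparison of Year 1 with Year 2 inside a school has only binomial error left to be judged against. Any further year-to-year variation within schools goes uncounted, the standard error of the intervention-by-year term is too small, and its test rejects too often.

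At stake is the subgroup message. Section 3.9 says that the results should inform the next year's programme, and a spurious difference between newly and previously invited year groups could misdirect attention within it.

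**Working it through.** **1. The plan's own figures.** The plan gives no variance, power or precision for the school-year interaction. Table 5 can be reproduced, with two-sided 5% assumed: for its first row, 2 × (1.960 + 1.282)² × 16² / 1² = 5,380 children; times 1 + 99 × 0.025 = 3.475, divided by 100, gives 187 clusters per arm, as stated. (An SD of 16.2 gives 192.) Every row compares arms with one school-level ICC, including the year-group rows with 30 children per cluster. None has a within-school component, so Table 5 does not settle this point.

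**2. Inputs.**
- Uptake 63%, so p(1 − p) = 0.63 × 0.37 = 0.2331 (section 3.7).
- Children per year group, m: 30 (Table 5), or 100 / 3 = 33.3 (section 3.7).
- ICC 0.025, the plan's base value (section 3.7).
- ICC near 0.10, from "We used an average vaccine uptake of 63.0% (SD 16.2%) in our power calculations", if that SD is read as the spread of uptake between schools: 0.162² / 0.2331 = 0.113. Removing binomial noise at the observed average of 110 children gives (0.113 − 1/110) / (1 − 1/110) = 0.104.
- Share of the school variance that is specific to a year group, s: **assumed**, 5% to 40%. The documents give no value.

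**3. Formula.** In units of p(1 − p), the model takes the variance of a year-group proportion, given its school, as (1 − ICC)/m. The true variance is s × ICC + (1 − ICC)/m. The ratio of true to model variance is therefore 1 + m × s × ICC / (1 − ICC). The standard error is too small by the square root of this ratio. The type I error of a nominal 5% single-contrast test is 2 × [1 − Φ(1.96 / √ratio)].

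Worked case: ICC 0.10, s = 40%, m = 33.3 gives 1 + 33.3 × 0.04 / 0.90 = 2.48; the root is 1.58 and the type I error 21.3%.

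**4. Results** (m = 30 first, then m = 33.3):

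| Year-specific share | ICC 0.025: SE ratio | ICC 0.025: type I error | ICC 0.10: SE ratio | ICC 0.10: type I error |
|---|---|---|---|---|
| 0% | 1.00 | 5% | 1.00 | 5% |
| 5% | 1.02, 1.02 | 5.4%, 5.5% | 1.08, 1.09 | 7.0%, 7.2% |
| 10% | 1.04, 1.04 | 5.9%, 6.0% | 1.15, 1.17 | 9.0%, 9.4% |
| 20% | 1.07, 1.08 | 6.8%, 7.0% | 1.29, 1.32 | 12.9%, 13.7% |
| 40% | 1.14, 1.16 | 8.7%, 9.1% | 1.53, 1.58 | 19.9%, 21.3% |

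**5. Simulation.** A random-intercept logistic model was fitted to 400 schools with three year groups of 33, with no true interaction. At a total logit variance of 0.5 (ICC about 0.10; 300 runs per setting), the test of letter by Year 1 rejected in 4.0%, 11.3%, 12.7% and 20.0% of runs for shares of 0%, 10%, 20% and 40%. At a logit variance of 0.11 (ICC about 0.025; 400 runs), it rejected in 3.0%, 7.0% and 7.5% for shares of 0%, 10% and 20%. With 300 runs, a rate near 12% has a Monte Carlo standard error of about 1.9 points.

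**6. What is not affected.** The mean of a school over k year groups carries the year-specific variance divided by k. A random school effect is estimated from the spread of those means, so it already contains that part. In the simulation at logit variance 0.5, the letter term (the effect in the other two year groups) had SE ratios of 1.03 to 1.05 with no trend in the year-specific share, and 1.05 when the share was zero. In a model for one year group at a time there is one count per school, so the school effect absorbs the year-specific part completely.

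**7. How far the contrast lies within schools.** Table 4 lists 228 infant and 205 junior schools: 433 of 1,726 (25%), and 117 + 104 = 221 of 454 in Hampshire. For these, Years 1-2 against Year 3 is a comparison between schools. Year 1 against Year 2 stays inside infant and primary schools. By inference from Table 1, Year 1 is the newly invited group in the Y1-Y3 areas, since Years 1 and 2 were covered in 2015/16.

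**The case against.** The strongest reply is that the target is narrow and the size is assumed. The affected text is one clause on secondary factors, without a decision rule. At the plan's own ICC the inflation is slight unless the year-specific share is large. The documents also point to influences that a school's year groups share: reminders go through the school's own message system, and the email text refers to a single vaccination session at the school. Section 3.10 is brief, and section 3.9 foresees that code will be written on interim data. All of this stands as a limit on size and urgency. It does not supply the missing error term: code written to section 3.10 as it reads would have none.

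A reader might infer three stronger things, and the documents support none of them.

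- **That the main results or the listed outcomes "in each individual year group" are compromised.** They are not, for the reasons in step 6, provided that the year-group outcomes are fitted one year at a time, as the 30-child clusters in Table 5 suggest.
- **That false positives could reach 28%.** That figure belongs to a joint 6-df test over seven year groups with an assumed year-specific SD of 0.3 logits. The plan specifies no such test, and only Essex offers Reception to Year 6 (473 + 37 + 41 = 551 of 1,726 schools). The single-contrast figure at that SD is 13%.
- **That the comparison lies wholly within schools.** The infant and junior schools make Years 1-2 against Year 3 partly a comparison between schools, where the school effect does protect.

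**Conclusion.** The point holds, within limits. As written, the model judges the within-school part of the intervention-by-school-year contrast against binomial error alone. Its standard error is too small if, and only if, year groups of a school vary beyond binomial error. That is plausible with about 30 children per year group, but the documents do not show it.

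The size depends on the assumed year-specific share and on which ICC is taken: close to nominal at 0.025 with a small share, and material near 0.10. The higher ICC depends on reading the SD of 16.2 points as a between-school SD. This is a weakness in one secondary, explanatory analysis and does not threaten the trial's main conclusions.

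**What to change.** Add one sentence to section 3.10: in any model that pools more than one year group per school, include a random effect for school by year group, or use standard errors clustered by school. The random effect can be estimated from the school-by-year counts, because the binomial variance is fixed by the model. It is not needed, and cannot be separated from the school effect, in models for a single year group.

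Keep the plan's focused contrast, newly invited against previously invited, and state which year groups fall on each side in each area, since the eligible years differ by area. A joint test over all years is not required and would dilute that question.

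The cost is one variance term or one option in the code, which fits the intention to write the code before the final data arrive. Intervals for the year-group interaction become wider by the SE ratios in the table, and only for that interaction. If there is no year-specific variation, the conclusions are essentially unchanged.

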We have conducted power calculations that indicate with this number of schools we would have 90% power to detect a 1% absolute increase in uptake, from 63% to 64% in children in years 1-3. The large number of schools available to us (~1700 schools), will enable us to have 90% power to detect an absolute change even if ICC is relatively high (

^{iv} Available at <https://www.compare-school-performance.service.gov.uk/download-data>

Table 5). Furthermore, we will have the power to detect our secondary outcomes e.g. uptake by year group.

It is possible, due to delays getting this project off the ground, that providers areas will need to go ahead with printing their letters before we have the approvals necessary to issue the randomisation. Our power calculations show that despite this we are likely to have sufficient schools to detect, with 90% power an absolute increase of 2% in uptake, with all but the highest estimates of ICC with just one or two providers (e.g South Essex NHS Partnership Trust, who have indicated a slightly later date for printing letters, has 451 schools. Clearly the size of the effect we have the power to detect will also depend on the impact of variation between strata in the trial (which are not accounted for in these power calculations).

Table 5. Power calculations for various scenarios, assuming no variation between strata.

Outcome	Scenario	Absolute % change able to detect	Power	ICC	Number clusters required in each arm	Total number of schools required
Primary outcome	Detecting lowest absolute effect	1%	90%	0.025	187	748
Primary outcome	Estimate of impact of ICC estimates on required minimum sample size	2%	90%	0.025	47	188
		2%	90%	0.05	81	324
		2%	90%	0.15	214	856
		2%	90%	0.25	347	1388
Secondary outcome	Analysis by individual year group (i.e. average size of the cluster 30)	2%	90%	0.025	78	312
		2%	90%	0.05	110	440
		2%	90%	0.15	240	960
		2%	90%	0.25	370	1480

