3.8. Randomisation

Randomisation will be undertaken by PHE Behavioural Insights Team. An up-to-date list of schools will be obtained from each area (or obtained from PHE and validated by the local team). Schools will be identified by their Unique Reference Number (School URN) to create the allocation list. Randomisation will be stratified by Provider and local authority. It is unlikely that we will know in advance (i.e. at the time of randomisation) which schools have email/SMS systems. (We anticipate this to be fairly common amongst schools.) We will therefore allocate all schools, irrespective of their available system, to one of the four trial arms. Randomisation will be carried out using a randomisation tool (e.g. ralloc or random number generator with schools ranked for allocation by random number order) in Stata, or other appropriate statistical-package to one of the four arms of the trial.

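### Naming each school's 2015/16 uptake as a covariate in the primary model would be a cheap gain in precision; its absence is not an error, and the size of the gain depends on two quantities the documents do not give

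*Combined protocol and SAP*

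**What the plan says.** Section 3.10 (Data analysis) plans an intention-to-treat logistic regression with the two interventions and their interaction. The model will also "include provider, local authority and school effect to take into account extra variation that was not explained by intervention and other confounder variables". School year and three inequality measures (deprivation quintile, free-school-meal eligibility, first language) are to be investigated in the models. Prior uptake is not named there, nor among the school characteristics to be linked in section 3.9, nor in the allocation strata of section 3.8: "Randomisation will be stratified by Provider and local authority".

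Prior uptake does appear elsewhere. For the non-randomised comparison of letters outside the trial, section 3.10 asks whether areas using a letter like the template had "greater change in uptake from to last year, compared to areas that used a dissimilar letter". Section 3.9 states that "School-level data by school year are routinely submitted to PHE", and section 3.7 that "We used 2015/16 data provided for Leicester, Leicestershire and Rutland", in that sentence to estimate cluster size.

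**The concern.** Schools are the units of allocation, so variation between schools drives the standard error of both main effects. A school effect puts that variation into the standard error but does not remove it. Last year's uptake in the same school is a natural predictor of this year's, and adjusting for it removes the part of the between-school variation that persists.

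All schools in the participating areas are already included, so precision cannot come from recruiting more of them. Section 3.7 says even a small rise in uptake would be worthwhile, and section 5.2 stresses the need to rule out an unintended fall. Both aims depend on a narrow confidence interval. The phrase about other confounders could cover prior uptake, but a covariate that is not named is not pre-specified.

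**Working it through.** **1. The plan's own figure.** Table 5, first row, gives 187 clusters per arm for a 1-point change at ICC 0.025. The formula is 2(1.960 + 1.282)²·SD²/δ² × [1 + (m − 1)·ICC]/m, with δ = 1 and m = 100. Two-sided alpha of 0.05 is assumed, since the plan states none.
- SD 16.0: 2 × 10.507 × 256 = 5,380; × 3.475/100 = 186.9, so 187.
- Printed SD 16.2: 191.7, so 192.

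No baseline term enters Table 5, so leaving one out contradicts no stated figure.

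**2. Coverage (Table 4, total 1,726).**
- Leicester, Leicestershire, Rutland: 91 + 19 + 241 = 351. This is an upper figure. The data cited in section 3.7 are tied to cluster size and leave out schools with fewer than 20 pupils in Years 1-3, so school uptake there is likely but inferred.
- Essex team: 473 + 37 + 41 = 551, giving 902. Appendix 2.1 shows Years 1-6 were offered the vaccine in Essex schools. Section 3.7 says "South Essex NHS Partnership Trust, who have indicated a slightly later date for printing letters, has 451 schools"; on that count the tier is 802 of 1,626.
- Hampshire non-junior: 454 − 104 = 350, giving 1,252. This takes the Appendix 2.2 letter to be from the Hampshire provider.
- Solent and Dorset Healthcare non-junior, by school type: 41 + 51 + 136 + 27 = 255, giving 1,507. Total minus junior gives 266 and 1,518, because Table 4 leaves 11 of these schools without a type. School-level data for these providers are not shown.
- No baseline: the 137 Wessex junior schools (104 + 12 + 8 + 4 + 6 + 3), if junior schools start at Year 3. Not shown: the 74 Boots UK schools.

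In 2015/16 the national offer covered Years 1-2 only (Table 1), so Wessex schools that teach Year 3 have a partial baseline.

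**3. Gain and break-even.** Gain = 1/(1 − f·r²). For a gain of 1.10, r = √[(1 − 1/1.10)/f]. The range of r, 0.3 to 0.8, is an assumption.

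| Schools with a baseline | f | r = 0.3 | 0.5 | 0.7 | 0.8 | r for a 10% gain |
|---|---|---|---|---|---|---|
| 351 | 0.203 | 1.02 | 1.05 | 1.11 | 1.15 | 0.67 |
| 902 | 0.523 | 1.05 | 1.15 | 1.34 | 1.50 | 0.42 |
| 1,252 | 0.725 | 1.07 | 1.22 | 1.55 | 1.87 | 0.35 |
| 1,507 | 0.873 | 1.09 | 1.28 | 1.75 | 2.27 | 0.32 |

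Using 1,518 changes no gain by more than about 0.02. With Essex at 451 schools, the second row runs from 1.05 to 1.46 and its break-even is 0.43. Simulated random-intercept logistic models with 1,252 baselines gave gains of 1.22 (r = 0.5) and 1.57 (r = 0.7), against 1.22 and 1.55 by formula.

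**4. Absolute scale.** Section 3.7 states: "We used an average vaccine uptake of 63.0% (SD 16.2%) in our power calculations". A child-level SD at 63% is 100√(0.63 × 0.37) = 48.3 points, so 16.2 is plausible only as a between-school SD. It is assumed here for all schools. With 863 v 863 schools:
- SE = 16.2√(2/863) = 0.78, and the 90% detectable main effect is 3.2415 × 0.78 = 2.53 points.
- If strata explain 30% of the variance (assumption): 2.53 × √0.7 = 2.12.
- From 2.53, a baseline gives 2.50 to 2.36 with 351 schools and 2.43 to 1.68 with 1,507, over r = 0.3 to 0.8.
- Power for 1 point is 25% without a baseline and 49% at best (1,507 schools, r = 0.8). If strata also explain 30%: SE = 0.78√(0.7 × 0.441) = 0.433, power about 64%.

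On the plan's ICC of 0.025 with a binary outcome, the starting value is 1.40 points. Reaching 1 point would need f·r² = 1 − (1/1.40)² ≈ 0.49, so r of about 0.75 with 1,507 schools. That ICC sits badly with 16.2, which implies about 0.10.

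**5. Chance imbalance.** The SE of the difference in prior uptake between two halves of the schools is at most 0.78 points, or 0.74 to 0.65 if strata explain 10% to 30%. Adjustment removes the part that persists.

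**The case against.** The strongest reply is that nothing is wrong. Randomisation protects the comparison, the plan leaves room for further covariates, and the deprivation-type terms may already carry some of what prior uptake would add. The benefit rests on an unknown r and unknown coverage: at r = 0.3 it is 9% at most, and with the Leicester-area schools alone it reaches 10% only at r of 0.67. One r is also applied to unlike programmes. Leicester and Essex were established pilots, whereas Table 1 shows no national school-year offer before 2015/16, so the Wessex baseline is a first-year rate and its r may be lower. Section 5.1 describes reduced resources and a tight timetable. All of this stands, and it limits the point to an optional gain of uncertain size. It does not remove the case for a term this cheap.

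A reader might infer three stronger things. The first is that the primary analysis is biased or invalid without the term; allocation is random, so it is not. The second is that the plan is inconsistent because it uses change from last year elsewhere. That analysis compares non-randomised areas, where prior uptake serves a different purpose. The third is that baseline uptake is already in hand for 351 schools or more. Section 3.7 shows only that 2015/16 data were provided and used for cluster size, and section 3.9 does not say that 2015/16 records are complete for every provider.

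**Conclusion.** The point holds as an improvement worth making, with medium confidence. The primary model does not name 2015/16 school uptake, and naming it would add precision at low cost. The gain could be negligible (1.02 times with 351 schools at r = 0.3) or substantial (1.75 times with 1,507 schools at r = 0.7). The break-even values of r are the firmest result, because they need no assumed correlation and no SD. They do depend on the coverage counts and on one r across providers.

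The detectable effects are upper figures, since they take 16.2 as the between-school SD with nothing explained by strata. On that SD the covariate does not restore the stated 90% power for 1 point at any r in the range, even if strata explain 30%. The power statement is a separate matter.

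**What to change.** Before any 2016/17 outcome data are seen, including the interim extract, confirm by provider which schools have 2015/16 uptake by URN. The stated purpose of that extract is "to enable the analysis to be fully planned (i.e. statistical analysis code written) ahead of the availability of final data", so fixing the covariate first simply keeps the choice free of outcome data. Then state in section 3.10:

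- School-level 2015/16 uptake (Years 1-3, or Years 1-2 where only those were offered) is a covariate in the primary model.
- The school effect is random. A fixed school effect would absorb the allocation.
- Schools without a baseline take a fixed fill-in value plus a missing-baseline indicator, so every randomised school stays in the intention-to-treat analysis.
- An adjusted absolute difference with its confidence interval is reported, by averaging model predictions over all schools under each allocation, because the conditional odds ratio shifts slightly with adjustment.
- The result without the term is a sensitivity analysis, and the numbers of schools with complete, partial and no baseline are given.

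If 2014/15 school-level data exist for the former pilot areas, r can be estimated there first and compared with the break-even values, though this says little about Wessex.

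The cost is one data extract, checks with each provider, two model terms and a little more reporting. The downside is little return if r is low or few schools have a baseline.
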